The percentage of subjects with unsolicited AEs within 30 days (Day 1-30) after each vaccine dose (overall doses) with its exact 95% CI will be tabulated by group and by MedDRA preferred term. Similar tabulation will be done for Grade 3 unsolicited AEs, for any causally related unsolicited AEs, for Grade 3 causally related unsolicited AEs and for unsolicited AEs resulting in a medically attended visit. The verbatim reports of unsolicited AEs will be reviewed by a physician and the signs and AEs will be coded according to the MedDRA Dictionary Version 20 for Adverse Reaction Terminology. Every verbatim term will be matched with the appropriate Preferred Term.

The percentage of subject with episode of spontaneous or excessive bleeding (AE of specific interest), during a 30-day follow-up period after each vaccination will be tabulated by group according to associated PT code presented in Section 12. The percentage of subjects with RSV-LRTI (AE of specific interest) from Dose 1 up to Day 365 and from Dose 1 up to study conclusion (Day 730) will be tabulated by group according to associated PT code presented in Section 12.

The percentage of subjects with SAE within 30 days (Day 1-30) after each vaccine dose with its exact 95% CI will be tabulated by group and by MedDRA preferred term. Similar table will be generated for SAE from Dose 1 up to Day 61, from Dose 1 up to Day 366 and from Dose 1 up to Day 731.

SAEs reported throughout the study and AE of specific interest will be described in detail.

The percentage of subjects using concomitant medication (any medication, any antipyretic/ analgesic and any antipyretic taken prophylactically, respectively) during the 7-day follow-up period (Day 1-7) and during the 30-day follow-up period (Day 1-30) will be summarized by group after each vaccine dose and overall.

For each group and for each hematology and biochemistry parameter:

- The percentage of subjects having hematology and biochemistry results below/above/within the local laboratory normal ranges will be tabulated by timepoint and toxicity grading scale.
- The maximum grading from Screening up to Visit 9 (Day 61) will be tabulated by grading the safety laboratory values according to toxicity criteria Grading scale adapted from [Division of AIDS, 2003], [Division of AIDS, 2004] and [Division of AIDS, 2007].

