## 12. ANNEX 2: RELEVANT PREFERRED TERMS FOR DETECTION OF AESI

Any of the below listed preferred term reported as an Expedited Adverse Event must be immediately escalated to the CRDL or Central Safety Physician to assess or confirm the need for an urgent IDMC review.

The list of preferred terms and associated PT codes is given below:

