**<each group>:**

RSV-Ld = Low dose ChAd155-RSV vaccine (5 x 10^9 vp)

RSV-Md = Middle dose ChAd155-RSV vaccine (1.5 x 10^10 vp)

RSV-Hd = High dose ChAd155-RSV vaccine (5 x 10^10 vp)

Placebo-Ld = Non-active control (0.5 ml)

Placebo-Md = Non-active control (0.15 ml)

Placebo-Hd = Non-active control (0.5 ml)

Potential AESI: AEs potentially related to spontaneous or excessive bleeding or LRTI will be identified based on the list of preferred terms described in section 11 –Annex

Please note the listing will be generated on group blinded at D61 and D366 analysis

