**CONFIDENTIAL**

204838 (RSV PED-002)  
Statistical Analysis Plan Final

**Template 33 Listing of AEs related to LRTI and association to RSV infection from vaccination dose 1 up to Day X visit/study end <Exposed Set>**

Group	Sub. No.	Age at onset (month)	Verbatim	Preferred term	MED type	Previous Dose	Day of onset	Start date	End date	Duration	Intensity	Causality	Outcome	Local RSV test result	Date of sample for local testing	Central test RSV A	Central test RSV B	Date of sample for central testing	AESI

RSV-Ld = Low dose ChAd155-RSV vaccine (5 x 10^9 vp)

RSV-Md = Middle dose ChAd155-RSV vaccine (1.5 x 10^10 vp)

RSV-Hd = High dose ChAd155-RSV vaccine (5 x 10^10 vp)

Placebo-Ld = Non-active control (0.5 ml)

Placebo-Md = Non-active control (0.15 ml)

Placebo-Hd = Non-active control (0.5 ml)

AESI: AEs of Special Interest - LRTI identified by the Investigator

\*AEs related to LRTI will be identified based on the list of preferred terms described in in section 12 –Annex 2

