**CONFIDENTIAL**

204838 (RSV PED-002)  
Statistical Analysis Plan Final

**Template 34 Listing of RSV-RTI cases identified according to WHO case definitions and RSV-LRTI reported as AESI from vaccination dose 1 up to Day X visit /study end <Exposed Set>**

Group	Sub. No.	Episode nb	Surveillance type	Start date of episode	End date of episode	SpO2	Respiratory rate	Local RSV test	Date of sample for local testing	Central test RSV A	Central test RSV B	Date of sample for central testing	RSV-RTI	RSV-LRTI	RSV-severe LRTI	RSV-very severe LRTI	All-cause LRTI	AESI	Hospitalization
													Yes/No	Yes/No	Yes/No	Yes/No	Yes/NO	Yes/No	Yes/No

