**CONFIDENTIAL**

204838 (RSV PED-002)  
Statistical Analysis Plan Final

**Template 35 Listing of AEs related to spontaneous or excessive bleeding together with hemoglobin and platelet count results from vaccination dose 1 up to Day 60 visit <Exposed Set>**

Group	Sub. No.	Age at onset (month)	Verbatim	Preferred term*	Previous Dose	Day of onset	Duration	Intensity	Start date	End date	AESI	Date of sample	Laboratory parameter	Raw result	Unit
XX	XX		XX	XX	XX	XX			XX	XX		XX	Hemoglobin		
													Platelet count		
												XX	Hemoglobin		
													Platelet count		
											...				

RSV-Ld = Low dose ChAd155-RSV vaccine (5 x 10^9 vp)

RSV-Md = Middle dose ChAd155-RSV vaccine (1.5 x 10^10 vp)

RSV-Hd = High dose ChAd155-RSV vaccine (5 x 10^10 vp)

Placebo-Ld = Non-active control (0.5 ml)

Placebo-Md = Non-active control (0.15 ml)

Placebo-Hd = Non-active control (0.5 ml)

\*AEs related to spontaneous or excessive bleeding will be identified based on the list of preferred terms described in section 12 –Annex

AESI: AEs of Special Interest – Spontaneous or excessive bleeding identified by the Investigator

CONFIDENTIAL

204838 (RSV PED-002)  
Statistical Analysis Plan Final

**Template 36 Listing of adverse events, SAEs and solicited symptoms leading to withdrawal from the study or treatment from vaccination dose 1 up to Day X visit/study end <Exposed Set>**

Group	Subject No.	Country	Gender	Race	AE Description	SAE	Causality	Outcome	Type of discontinuation

RSV-Ld = Low dose ChAd155-RSV vaccine ( $5 \times 10^9$  vp)  
RSV-Md = Middle dose ChAd155-RSV vaccine ( $1.5 \times 10^{10}$  vp)  
RSV-Hd = High dose ChAd155-RSV vaccine ( $5 \times 10^{10}$  vp)  
Placebo-Ld = Non-active control (0.5 ml)  
Placebo-Md = Non-active control (0.15 ml)  
Placebo-Hd = Non-active control (0.5 ml)

**Template 37 Number and percentage of subjects with anti-RSV-A neutralising antibody titre equal to or above <cut-off> and GMTs <PPS for analysis of immunogenicity at Day X>**

				≥cut-off unit				GMT				
						95% CI			95% CI			
Antibody	Group	Timing	N	n	%	LL	UL	value	LL	UL	Min	Max
Anti-RSV-A Neutralizing Antibody	<each group>	PRE										
		PI(D31)										
		PII(D61)										
		PII(D366)										

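### SAP 6.4.1.1 ties both AESI percentages to a preferred-term screening list without limiting the count to AESIs reported by the investigator

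*SAP*

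**What the plan says.** **Definitions.** Protocol 9.1.5 defines the two AESIs by clinical content. Section 9.1.5.1 covers an episode of spontaneous or excessive bleeding within 30 days of a vaccination. Section 9.1.5.2 covers an LRTI associated with RSV, diagnosed by the investigator with the help of a local RSV test. Both are reported as AESIs through the expedited route in 9.4.3.

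**Analysis rule.** SAP 6.4.1.1 has two consecutive sentences, one per AESI. Each names the AESI and then says that the percentage "will be tabulated by group according to associated PT code presented in Section 12". Neither mentions the investigator's AESI report, and the RSV-LRTI sentence mentions no RSV result.

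**The list.** SAP Section 12 (Annex 2) has four sub-lists: haematoma, haemorrhage, thrombocytopenia and LRTI. It is introduced as an escalation screen: "Any of the below listed preferred term reported as an Expedited Adverse Event must be immediately escalated to the CRDL or Central Safety Physician".

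**Templates.**
- Template 28, the shell for the bleeding percentage, names the AESI in its title and classifies by system organ class and PT.
- Template 32 labels list matches as potential AESIs: "AEs potentially related to spontaneous or excessive bleeding or LRTI will be identified based on the list of preferred terms". Its pointer reads section 11, but the only such list is in Section 12.
- Template 33: "AEs related to LRTI will be identified based on the list of preferred terms". A separate AESI column is footnoted "LRTI identified by the Investigator".
- Template 34 covers "RSV-LRTI reported as AESI from vaccination dose 1", with no PT condition.
- Template 35: "AEs related to spontaneous or excessive bleeding will be identified based on the list of preferred terms". A separate AESI column is footnoted "Spontaneous or excessive bleeding identified by the Investigator".

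**The concern.** A screening list is built to be broad, so that possible cases are looked at quickly. An endpoint count should instead follow the endpoint's definition. The SAP holds both concepts, list match and investigator-identified AESI, and keeps them in separate columns of its listings. The percentages in 6.4.1.1 refer only to the list.

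The bleeding AESI is a component of the primary endpoint (protocol 11.1), and the RSV-LRTI AESI is a secondary endpoint (11.2). If the list acts as the selector, these percentages can include infants who do not meet protocol 9.1.5 and omit infants who do.

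**Working it through.** There is no planned figure to reproduce. The check sets the rule, the list and the definitions side by side.

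**1. Does any text make the investigator's report the selector?** SAP 6.4.1.1 does not. Template 28 has no footnote that does so, and its example rows (diarrhoea, teething and so on) are not bleeding terms, so they do not help. The study-specific templates contain no percentage table for the RSV-LRTI AESI. Protocol 11.8.1 says only that AESIs will be described, and SAP Section 9 lists no PT-based rule among its changes.

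**2. What would the list add if it were the selector?**
- *LRTI sub-list.* It has 14 terms. Three name RSV (RSV pneumonia, RSV bronchiolitis, RSV bronchitis), so 14 − 3 = 11 do not. Two of the 11, respiratory tract infection and its viral form, are not limited to the lower tract. A non-RSV pneumonia matches the list but not 9.1.5.2. The 11 of 14 is a share of dictionary terms, not of events.
- *Petechiae* is in the haemorrhage sub-list. Protocol 6.6.13 has every infant's limb examined at Day 1 and Day 31 for petechiae induced by the tourniquet, and leaves it to the investigator whether to report these as AEs. One recorded as an ordinary AE would match the list without being reported as an AESI.
- *Thrombocytopenia sub-list.* Of 9 terms, 8 (all but thrombocytopenic purpura) need no bleeding episode. Protocol 9.1.5.1 names bleeding only, 6.6.11.2 links the AESI also to a low platelet count, and holding rule 1d requires bleeding and thrombocytopenia together. The SAP does not say which AESI this sub-list serves.

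**3. What would the list omit?** Epistaxis is not listed, and bronchiolitis is listed only in its RSV form. That a verbatim would be coded to epistaxis or to bare bronchiolitis is an assumption. If it were, the event falls outside the Section 12 codes whether those codes select or only display. An RSV-LRTI of this kind would still appear in Template 34. A bleeding AESI of this kind would also be missing from Template 35, which identifies events by the same list.

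**4. What does one infant change?** The SAP's exact (Clopper-Pearson) 95% intervals, at the smallest and full group sizes of about 8 and 16, are:

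| Count | Percentage | Exact 95% CI |
|---|---|---|
| 0/16 | 0% | 0 to 20.6% |
| 1/16 | 6.3% | 0.2 to 30.2% |
| 0/8 | 0% | 0 to 36.9% |
| 1/8 | 12.5% | 0.3 to 52.7% |

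For zero events the upper limit is 1 − 0.025^(1/n): n = 16 gives 20.6% and n = 8 gives 36.9%. For one event the lower limit is 1 − 0.975^(1/n): 0.2% and 0.3%.

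**The case against.** The strongest reply is grammatical. In 6.4.1.1 and in the Template 28 title, the AESI is the thing counted and the PT is how it is classified. Read this way, generic terms such as pneumonia belong in the list, because an investigator can report an RSV-positive pneumonia whose PT does not name RSV. This reading is open, so it cannot be said that the SAP sets no condition at all. But the SAP never states it, and in Templates 32, 33 and 35 the same list identifies events. Template 28's top row counts a symptom whatever its PT, but the same footnote stands in the general unsolicited-AE shell (Template 22) and does not say which events enter the table. A display confined to Section 12 codes still has no place for an unlisted term.

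Second, Section 12 speaks of terms in expedited reports, which under protocol Table 20 means SAEs and AESIs. If that limit carried over, an ordinary-AE petechia would not count. SAP 6.4.1.1 does not carry it over, and a serious non-RSV pneumonia would pass it anyway.

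Third, much can be traced elsewhere. Template 34 lists reported RSV-LRTI AESIs. Templates 33 and 35 show the investigator's flag beside each match. AESIs are also to be described in detail. This limits the harm but does not correct the percentages.

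A reader might also infer that site or procedure terms are mistakes, or that haemorrhagic pneumonia, which is in both the haemorrhage and the LRTI sub-lists, is double counting. The documents support neither. Excessive bleeding at an injection or catheter site can meet 9.1.5.1, and one RSV-associated haemorrhagic pneumonia could meet both definitions.

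**Conclusion.** The rule is wrong as written. It ties two endpoint percentages to a screening list and does not say that the investigator's AESI report decides who is counted. Selection by PT is the likelier reading given the listing footnotes, but it is not the only one. Under that reading the percentages can include infants without the AESI. Under either reading they can omit a reported AESI coded outside the list.

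The effect is bounded. All these analyses are descriptive (SAP Section 7). The qRT-PCR case-definition analysis of RSV-LRTI (SAP 6.3 and 11.3.6) and Template 34 are not affected. After the 30-day windows, non-serious AEs are mostly not collected, so late over-counting of RSV-LRTI would mainly be serious non-RSV LRTI.

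A reader might infer that the reported percentages will be inflated by some amount. The documents give no rate for tourniquet petechiae, low platelets without bleeding or non-RSV LRTI, so neither an expected number nor a net direction can be stated. The table above shows only what one infant does. SAP Section 10 places the table index and standard shells outside the document, so a selection rule held there cannot be excluded.

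**What to change.** In SAP 6.4.1.1, select events for both percentages by the investigator's AESI report (protocol 9.1.5 and 9.4.3), whatever the PT. For RSV-LRTI, require the RSV association. Then display the selected events by PT.

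Keep the Section 12 search as a separate output labelled potential AESI. State which sub-lists map to which AESI, including thrombocytopenia.

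Make Template 35 list every bleeding AESI flagged by the investigator as well as the list matches. Template 34 already does this for RSV-LRTI.

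The cost is SAP wording, one selection variable in two tables and a footnote change in one listing. The investigator's flag is already collected, so no new data are needed.

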During a study carried out in adult subjects (RSV001), a mild non-clinically significant drop in hemoglobin was noted following vaccination with another adenoviral vector (PanAd3-RSV) without clinical signs and with a reversal towards baseline values over time [[RSV001 Interim Study Report](#), 2014]. In the repeat dose toxicology study in rabbits using the ChAd155-RSV vaccine, a transient non-clinically significant drop in platelets was noted post IM vaccination (maximal drop of platelet observed 24 hours after vaccination; refer to the current IB for further details). In light of these data, a clinical examination with special attention given to the detection of spontaneous bleeding or easy bruising and evidence of bruising or petechiae will be performed by the investigator/study staff on Day 1, Day 3, Day 7, Day 31, Day 33 and Day 37. The visits on Day 3 and Day 33 may be replaced by a phone call by the investigator/study staff to inquire of the infants' general health and to solicit reports of a rash, spontaneous bleeding or easy bruising. On Day 1 after each vaccination, special attention will also be given to the detection of petechiae or evidence of petechiae induced by the tourniquet. This special attention to detection of petechiae or evidence of petechiae induced by the tourniquet will also be given on Day 7 and Day 37 in case hematology testing will be performed on that day. Subjects' parent(s)/ legally acceptable representative(s) (LAR[s]) will be instructed to contact the investigator/study staff if their child presents symptoms of spontaneous bleeding or easy bruising or if their child develops a rash in the month following vaccination, in order to detect any thrombocytopenic petechiae or purpura. The

investigator will, based on his/her medical judgement, appropriately investigate infants with clinical suspicion of low platelets.

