A transient non-clinically significant drop in platelets was noted post IM vaccination in a preclinical study with the ChAd155-vector (refer to the current IB for further details). Furthermore, in Ebola Phase I studies in adults investigating a similar adenoviral vectored vaccine (ChAd3-EBO-Z), transient decreases in thrombocyte counts were also observed. These decreases occurred mostly on Day 1 after vaccination and generally returned to baseline by Day 7. Although most of these decreases remained within the normal range, the per protocol criteria for thrombocytopenia (i.e. thrombocyte count of $< 150 \times 10^3/\mu\text{L}$) were met for 2.6% (7 out of 270) of the vaccinated subjects. None of the decreases in thrombocyte counts or the cases of thrombocytopenia were clinically significant (i.e. no clinical signs or symptoms suggestive of increased tendency to bleeding were reported in any of the subjects; refer to the current IB of recombinant chimpanzee adenovirus Type 3-vectored Ebola Zaire vaccine for further details). Although the mechanism underlying these decreases currently remains unclear, it is well described in literature that, post intravenous administration, adenovirus activates platelets and induces platelet-leukocyte aggregate formation, causing an associated increase in platelet and leukocyte-derived microparticles [[Othman](#), 2007; [Stone](#), 2007].

No significant safety concerns were identified up to 30 days post Dose 2 in study RSV PED-001 with the ChAd155-RSV vaccine in healthy adults aged 18 to 45 years (refer to Section [1.1.6](#) and to the current IB).

All available safety information from clinical and pre-clinical studies was evaluated by GSK's Safety Review Team. It was concluded that the available information did not pose an immediate safety concern, since the decreases seen were transient and not clinically significant. Nevertheless, since this is the first time the ChAd155-RSV vaccine is administered to infants and to ensure a maximum safety follow-up, a safety monitoring plan has been put in place (refer to Section [1.2.4](#)).

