- For eosinophils, basophils, and monocytes, summary statistics (min, max, standard deviation, mean and median) will be presented as there is no grading provided for these parameters.

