**<each group>:**

RSV-Ld = Low dose ChAd155-RSV vaccine (5 x 10^9 vp)  
 RSV-Md = Middle dose ChAd155-RSV vaccine (1.5 x 10^10 vp)  
 RSV-Hd = High dose ChAd155-RSV vaccine (5 x 10^10 vp)  
 Placebo-Ld = Non-active control (0.5 ml)  
 Placebo-Md = Non-active control (0.15 ml)  
 Placebo-Hd = Non-active control (0.5 ml)

For each dose:

N = total number of subjects with the corresponding administered dose  
 n/% = number/percentage of subjects took the specified type of concomitant medication at least once during the considered period

For Overall/dose:

N = number of administered doses  
 n/% = number/percentage of doses after which the specified type of concomitant medication was taken at least once during the considered period

For Overall/subject:

N = total number of subjects with at least one administered dose  
 n/% = number/percentage of subjects who took the specified type of concomitant medication at least once during the considered period

95%CI = Exact 95% confidence interval; LL = lower limit, UL = upper limit

**Template 24 Distribution of change from baseline in hematology and biochemistry with respect to normal laboratory ranges <Exposed Set>**

Laboratory parameter	Timing	Range indicator at Baseline (SCR)	Range indicator at timing	<each group >		
				N	n	%
Alanine Aminotransferase	PI(D2)	Unknown	Unknown			
			Below			
			Within			
			Above			
		Below	Unknown			
			Below			
			Within			
			Above			
		Within	Unknown			
			Below			
			Within			
			Above			
		Above	Unknown			
			Below			
			Within			
			Above			
	PI (D8)	...				
	PI (D31)					
	PII (D32)	...				
	PII (D38)	...				
	PII (D61)	...				
	UNSCH1					
	UNSCH2					
	...	...				
Aspartate Aminotransferase	...	...				
Creatinine	...	...				
Hemoglobin						
Leukocytes (White Blood Cells)	...	...				
Neutrophil						
Platelets	...	...				

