**Template 26 Descriptive statistics table on eosinophils, basophils, and monocytes counts for subjects <Exposed Set>**

		Each Group N=			
		95% CI			
Parameters	Timing	Parameter	Value	LL	UL
Eosinophils	SCR	n			
		Mean			
		95% CI			
		Q1			
		Median			
		Q3			
		Min/Max			
	PI(D2)				
	PI (D8)				
	PI (D31)				
	PII (D32)				
PII (D38)					
Basophils					
Monocytes					

RSV-Ld = Low dose ChAd155-RSV vaccine ( $5 \times 10^9$  vp)  
 RSV-Md = Middle dose ChAd155-RSV vaccine ( $1.5 \times 10^{10}$  vp)  
 RSV-Hd = High dose ChAd155-RSV vaccine ( $5 \times 10^{10}$  vp)  
 Placebo-Ld = Non-active control (0.5 ml)  
 Placebo-Md = Non-active control (0.15 ml)  
 Placebo-Hd = Non-active control (0.5 ml)  
 N = number of subjects in each group  
 n= Number of subjects with result available  
 SD=Standard Deviation  
 Q1, Q2 and Q3 = 1st, 2nd (median) and 3rd quantiles  
 Min/Max = Minimum/Maximum  
 95% CI = exact 95% confidence interval, LL = Lower Limit, UL = Upper Limit

**Figure 2** Individuals results of hemoglobin levels in < group> <Exposed Set>

Note: This figure is shown as an example.

**Template 27 Exploratory comparisons between groups in terms of percentage of subjects reported any Grade 2/3 AE and/or any fever >38.5°C and/or any vaccine-related SAE during the 7-day (Days 1-7) post-vaccination period <Exposed Set>**

								Difference in percentage (Group 1 minus Group 2)			
										95 % CI	
Group 1	N	n	%	Group 2	N	n	%	Difference	%	LL	UL
RSV_Ld				Placebo_Ld				RSV_Ld – Placebo_Ld			
RSV_Md				Placebo_Md				RSV_Md – Placebo_Md			
RSV_Hd				Placebo_Hd				RSV_Hd – Placebo_Hd			

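### The SAP plans range and grade tables for platelets and haemoglobin, but no summary statistics, numeric change from pre-dose value or vaccine-placebo difference, so a moderate fall within the normal range would barely show

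*SAP*

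**What the plan says.** SAP days are protocol days plus one, so the 24-hour draws are protocol Days 1 and 31 and SAP Days 2 and 32.

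- **Range categories.** For each graded parameter, SAP 6.4.1.1 plans percentages of subjects with "results below/above/within the local laboratory normal ranges will be tabulated by timepoint and toxicity grading scale". Template 24 is titled "Distribution of change from baseline in hematology and biochemistry with respect to normal laboratory ranges", but it cross-tabulates below/within/above at Screening against the same categories later. No numeric change appears in it.
- **Grades.** "The maximum grading from Screening up to Visit 9 (Day 61) will be tabulated by grading the safety laboratory values". Template 25 is the matching grade table.
- **Numeric summaries.** Only three cell types get these: monocytes, eosinophils and basophils. The SAP gives its reason: "summary statistics (min, max, standard deviation, mean and median) will be presented as there is no grading provided for these parameters".
- **Between groups.** SAP 6.4.1.2 compares Grade 2/3 AEs, fever and vaccine-related SAEs. No laboratory parameter is included.
- **Individual data.** Figure 2 is titled "Individuals results of hemoglobin levels in < group> <Exposed Set>", with the remark "Note: This figure is shown as an example". Appendix Table IV.A lists haematology values. Templates 31 and 35 list platelet and haemoglobin results for unscheduled visits and bleeding cases. SAP 8.1 withholds individual listings at the Day 61 and Day 366 analyses.
- **Escalation.** Protocol 11.4 calculates a 95% CI for the vaccine-placebo difference in mean platelets at protocol Day 31, on the first 16 infants of a cohort, to support the IDMC's escalation recommendation. The SAP does not carry this over.

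**The concern.** The protocol describes the kind of signal it is watching for. In rabbits given this vaccine there was a transient platelet fall ("maximal drop of platelet observed 24 hours after vaccination", Protocol 1.2.4.3). In adults given a related chimpanzee-adenovirus Ebola vaccine, falls came mostly on Day 1 and generally reversed by Day 7. Of these, Protocol 1.3.1 says: "Although most of these decreases remained within the normal range"; 7 of 270 (2.6%) met the criterion of a count below 150,000. A mild haemoglobin fall was seen with another adenoviral vector.

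The sampling fits that pattern: a draw 24 hours after each dose in every infant, a Screening baseline, and a sample just before Dose 2. Retesting at Day 7 or 37 is triggered only by a platelet fall of Grade 1 or worse, so a fall that stays in range gets no scheduled follow-up sample. The 24-hour values are then the main information on it, and the planned tables record them as within range.

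At stake is what the trial can report on its leading safety question before a later study in seronegative infants. A consistent moderate fall could appear as almost no abnormalities. If there is no effect, the tables supply no estimate and interval to show how large a fall has been excluded.

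**Working it through.** **Inputs from the documents.** Platelets normal with mean 300,000 and SD 75,000 per mm³; focus range 150,000-450,000; margin 110,000; 8 per group at the escalation look (all Protocol 11.4). Grade 1 starts below 150,000 (Protocol Appendix C). Vaccine against placebo totals are 48 v 48 at full enrolment and 32 v 32 at the permitted minimum (8 + 8 + 16 per arm).

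**Assumptions.** The size of a within-range drop (the documents give none; 25,000 to 110,000 tried) and the within-infant correlation r between pre- and post-dose counts (0.5 to 0.7).

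**1. The plan's own figure.** Power to rule out 110,000 at 8 v 8, one-sided 0.025, true difference zero, by normal approximation:
Φ(110,000 / (75,000 × √(2/8)) − 1.96) = Φ(2.933 − 1.96) = 83.5%, against 84% stated. The figure is not in dispute; the same distribution is used below.

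**2. Share below 150,000.** Placebo: Φ((150 − 300)/75) = Φ(−2) = 2.3%. After a mean drop of 50,000: Φ((150 − 250)/75) = Φ(−1.33) = 9.1%. Of 16 infants that is 0.4 against 1.5 expected, and about 91% of vaccinees remain at or above 150,000.

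**3. Power at a 50,000 drop.** Counts: Fisher exact test, two-sided 5%, by enumeration. Mean change: two-sample t test with SD = 75,000 × √(2(1 − r)), which is 75,000 at r = 0.5 and about 58,100 at r = 0.7.

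| Size | Counts below 150,000 | Mean change (r = 0.5 to 0.7) |
|---|---|---|
| 16 v 16 | 0.8% | 45-65% |
| 32 v 32 | 3% | 75-92% |
| 48 v 48 | 12% | 90-99% |

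**4. Other drops at 16 v 16** (mean change at r = 0.5, the less favourable end).

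| Assumed drop | Vaccinees below 150,000 | Expected, vaccine v placebo | Counts | Mean change |
|---|---|---|---|---|
| 25,000 | 4.8% | 0.8 v 0.4 | 0.0% | 15% |
| 75,000 | 15.9% | 2.5 v 0.4 | 7% | 78% |
| 110,000 | 29.7% | 4.8 v 0.4 | 42% | 98% |

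At 110,000 and 48 v 48 the counts alone reach 97%.

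**5. Check without an assumed drop.** If infants cross 150,000 at the related-vector adult rate of 7/270, the chance of at least one such infant is 1 − (263/270)¹⁶ = 34% in a group of 16 and 72% in 48 vaccinees. Two groups of 16 in three would show none.

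**6. Precision of the proposed estimate.** 95% CI half-width = t × SD × √(2/n):
- 8 v 8: 2.145 × 75,000 × 0.5 = 80,400 (r = 0.5); 62,300 (r = 0.7)
- 16 v 16: 54,200; 41,900
- 48 v 48: 30,400; 23,500

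**The case against.** **The planned tables match the endpoint.** The primary endpoint is the occurrence of haematological abnormalities, and range and grade tables answer that. This stands. The proposal is an addition, and those tables should stay.

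**The stronger reading fails.** A reader might infer that the final analysis cannot see a platelet or haemoglobin effect at all. The documents do not support that. Figure 2 plots individual haemoglobin, Appendix Table IV.A lists every value by study end, the iSRC and IDMC review unblinded laboratory data, and Protocol 11.4 estimates a mean platelet difference for escalation. A drop at the 110,000 margin would largely show in the tables. What remains is narrower: listings are not estimates and are withheld at Day 61, when the primary safety data are analysed, and the escalation statistic covers only part of a cohort.

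**The expected effect should not be overstated.** A reader might also infer that a within-range fall is expected with this vaccine, or for haemoglobin. The within-range statement concerns platelets with another vector. The haemoglobin fall is called mild, with nothing said about normal range. Adults given this vaccine had no significant platelet reductions, and the earlier falls are described as not clinically significant.

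**No laboratory test is planned.** True: the study is descriptive. Power is used here only to measure how much information categorising discards. The real gap is the missing estimate and interval.

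**The remedy is weak in small groups.** Steps 1 and 2 may have 8 per group. At 8 v 8, mean change has only 24-36% power for a 50,000 drop, and pooling spans a ten-fold dose range. Both points stand and should be stated with the results.

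**The baseline is a matter of choice.** Template 24 compares post-Dose-2 values with Screening, which can be up to 30 + 36 = 66 days old. Screening is the only baseline before any exposure; the pre-Dose-2 sample isolates the second dose. Neither is wrong.

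**The full table list is not visible.** SAP section 10 refers to a TFL table of contents and standard mock tables held elsewhere. The point therefore covers only the SAP text and its study-specific templates.

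**Conclusion.** The point holds in a limited form. In the visible SAP, platelets have no summary statistics, numeric change or vaccine-placebo difference, and haemoglobin has none beyond an example plot of individual levels. Three ungraded cell types do receive numeric summaries.

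The planned tables suit large falls and poorly suit moderate ones. For a 50,000 platelet drop, counts have about 1%, 3% and 12% power at 16, 32 and 48 per arm, against 45-65%, 75-92% and 90-99% for mean change. These figures rest on the protocol's normal distribution, an assumed drop and an assumed correlation. The ordering is the same for every drop from 25,000 to 110,000 tried at 16 v 16. No corresponding calculation was made for haemoglobin, because the documents give no distribution for it.

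This is an inexpensive improvement to reporting on the stated safety concern. It does not show that the plan fails its endpoint or that safety monitoring is blind.

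**What to change.** In SAP 6.4.1.1 add, for platelets and haemoglobin by group, descriptive mean change with 95% CI from Screening to SAP Day 2 and from the SAP Day 31 pre-Dose-2 sample to SAP Day 32. Change from Screening may be shown alongside for Day 32.

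In SAP 6.4.1.2 add the vaccine-minus-placebo difference in these changes with 95% CI, per step and pooled, labelled exploratory. Add an individual platelet plot matching Figure 2. Keep the range and grade tables.

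State the limited precision beside the results. For platelets the half-width is about 62,000-80,000 at 8 v 8 and 42,000-54,000 at 16 v 16.

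Cost: SAP wording, one table and one figure. Every sample is already scheduled, so no study procedure changes.
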